6.1 Pre-Operative Plan

Following informed consent and randomization, study staff will record baseline patient demographics (including baseline NRS values for pain at rest, age, weight, gender, ASA physical status) from the electronic medical record and/or during the patient interview.

NRS pain scores at rest will be measured at the following time points: arrival to post-anesthesia care unit (PACU), prior to PACU discharge, every 4 hours beginning on arrival to patient room. Pain scores will be measured until hospital discharge from the time of the initial assessment in

the recovery room (PACU). All NRS pain scores will be recorded by registered nurses per standard protocol.

Regional Block – Both CISB and SISB:

Based on our current total joint regional anesthesia pathway (MC1156-462rev0115 and MC1156-1321rev1015), all patients will be provided (unless contraindicated and at the discretion of the attending anesthesiologist) a combination of oral analgesic medications preoperatively:

- 1) Tylenol 1 gram – at least 6 hours since last dose
- 2) Celecoxib 400 mg – for patients 18-64 years old and CrCl > 50 mL/min (if lab is available)
- 3)
 - a. Oxycodone (immediate release)
 - i. 5-10 mg once for patients 18-64 years old
- 4) Scopolamine Transdermal patch: 1.5mg - Apply to skin behind ear for 24 hours for high-risk patients (history of motion sickness or postoperative nausea vomiting). This is at the discretion of the anesthesiologist.

Local Infiltration Analgesia (LIA):

- 1) Tylenol 1 gram – at least 6 hours since last dose
- 2) Celecoxib 400 mg – for patients 18-64 years old and CrCl > 50 mL/min (if lab is available)
- 3)
 - a. Oxycodone (immediate release)
 - i. 5-10 mg once for patients 18-64 years old
- 4) Scopolamine Transdermal patch: 1.5mg - Apply to skin behind ear for 24 hours for high-risk patients (Hx: motion sickness or postoperative nausea vomiting). This is at the discretion of the anesthesiologist.

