4.1 Inclusion Criteria

1. Adult patients with an American Society of Anesthesiologists (ASA) physiological status I-III
2. Patients presenting for unilateral primary total shoulder arthroplasty (includes anatomic and reverse total shoulder arthroplasty).
3. Patients 18 years of age and older
4. Able to provide informed consent for him or herself

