7.1 Sample Size Determination

The sample-size for this study was determined in order to provide statistical power of >90% to detect a difference of 3 units for the primary endpoint (OBAS on POD1). Based on a previous study, we hypothesize that the standard deviation of OBAS will be approximately 3 units.⁴⁴ Under this assumption, an effective sample-size of N=39 per group will provide statistical power of >90% to detect a difference between groups of 3 units using a two-sided, alpha=0.017 (multiple-comparison adjusted for 3 groups), non-parametric test. In addition, for the key secondary endpoint of pain (NRS), this sample-size will provide statistical power of 80% to detect a difference of 0.75 standard deviations (approximately 2.25 units on the NRS). In order to accommodate attrition of approximately 10% (due to canceled surgery, failed block, etc.) we propose a total sample-size of N=129 (43 patients per group).

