7.2 Statistical Methods

Descriptive Statistics

Baseline characteristics will be summarized using mean and standard deviation for continuous variables that have a normal Gaussian distribution, and median and interquartile range for continuous variables with a non-normal distribution. Frequencies and percentages will be used to summarize categorical baseline characteristics. Baseline characteristics will be compared across groups using analysis of variance, or the Kruskal-Wallis test for continuous variables and the chi square test for categorical variables.

The primary aim of this study is to assess whether continuous interscalene nerve block provides superior analgesic benefit via OBAS compared to single injection interscalene blockade and local infiltration analgesia on POD 1 for primary total shoulder arthroplasty. In order to test this hypothesis, the will be compared across groups using ANOVA (or the Kruskal-Wallis test). Supplemental pairwise comparisons will be performed using two-tailed tests with $\alpha=0.017$ (Bonferroni adjusted) used to denote statistical significance. Similar analyses will be performed for secondary endpoints of pain and total additional opioid medications (moeq) until hospital discharge.

NRS pain scores measured at arrival to PACU, PACU discharge, and every 4 hours until time of hospital discharge following surgery will be analyzed using repeated measures ANOVA with pairwise treatment comparisons performed using linear contrasts.

Postoperative complications will be compared across groups using the chi-square test and hospital length of stay (number of postoperative days) will be compared across treatment groups using the Kruskal-Wallis test with supplemental pairwise comparisons performed using the rank sum test. Similar analyses will be performed for additional endpoints collected at the 12-16 week follow-up visit including NRS pain scores and SF-12 scales.

Our primary analysis will be performed based on the intention to treat. All calculated p-values will be two sided. For the overall analyses comparing across all 3 treatment groups simultaneously p-values less than 0.05 will be considered statistically significant. For supplemental pairwise treatment group comparisons p-values less than 0.017 (Bonferroni adjusted) will be considered statistically significant. The statistical analysis will be performed using SAS version 9.4 (SAS Institute Inc., Cary, North Carolina, United States).

Handling of Missing Data

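### Optional small precision gain: 7.2 could prespecify a linear model for OBAS with arm and age group; the unadjusted comparison is valid as it stands

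*Combined protocol and SAP*

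**What the plan says.** Section 6.1 gives two preoperative drug lists, one for CISB and SISB and one for LIA. Both list oxycodone as "5-10 mg once for patients 18-64 years old" and celecoxib "for patients 18-64 years old and CrCl > 50 mL/min (if lab is available"). Acetaminophen is the only oral analgesic listed without an age limit. Section 4.1 admits "Patients 18 years of age and older", so patients on both sides of the limit can enrol. Section 6.1 also records "baseline NRS values for pain at rest, age, weight, gender, ASA physical status" at baseline.

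Age is not used after that. Section 5.3 randomizes in blocks of six and names no stratification factor. Section 7.2 says that the groups "will be compared across groups using ANOVA (or the Kruskal-Wallis test"), with no covariate, and adds: "Supplemental pairwise comparisons will be performed using two-tailed tests with" a threshold of 0.017. The subgroups in 7.3 are treatment per protocol and reverse versus anatomic arthroplasty.

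Section 7.1 sizes the trial at 39 evaluable patients per arm for more than 90% power to detect 3 OBAS units. It assumes that the "standard deviation of OBAS will be approximately 3 units" and uses "alpha=0.017 (multiple-comparison adjusted for 3 groups), non-parametric test".

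**The concern.** Within every arm, the listed oral premedication changes at age 65. OBAS combines pain intensity, opioid side effects and satisfaction, and the age-limited drugs are an opioid and an anti-inflammatory analgesic. If age group is related to OBAS, for this or any other reason, the unadjusted analysis leaves that variation in the error term. A baseline term in the model would remove it and narrow the intervals for the three pairwise differences. What is at stake is interval width, not validity. Age group is a reasonable candidate because the protocol itself conditions treatment on it and the data are already collected.

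**Working it through.** **Inputs.** From 7.1: SD 3, 39 evaluable per arm, two-sided 0.017 per pair, target 3 units. Not in the documents: R², the share of OBAS variance explained by age group, taken as 0 to 0.10; and the share of patients aged 65 or over, taken as 0.5 or 0.75 in simulations.

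**The plan's own figure.** The standard error of a pairwise difference is 3 × √(2/39) = 0.679. Power for 3 units is 97.9% by the normal approximation and 97.6% by noncentral t with the pooled three-arm error (117 − 3 = 114 df). A simulated rank-sum test gives about 96.5%. All exceed the stated 90%.

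**Linear model with age group.** SE = 3 × √(1 − R²) × √(2/39), with 117 − 4 = 113 df.

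| R² | SE | Power, 3 units | Power, 2 units | Difference with 90% power |
|---|---|---|---|---|
| unadjusted | 0.679 | 97.58% | 69.86% | 2.52 |
| 0 | 0.679 | 97.58% | 69.85% | 2.52 |
| 0.01 | 0.676 | 97.7% | 70.4% | 2.51 |
| 0.05 | 0.662 | 98.2% | 72.4% | 2.46 |
| 0.10 | 0.645 | 98.6% | 75.1% | 2.39 |

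The SE falls by 1 − √0.95 = 2.5% and 1 − √0.90 = 5.1% at R² of 0.05 and 0.10. The half-width of a 98.3% interval, 2.42 × SE, goes from 1.65 to 1.60 and 1.56 units. Two units is not a target in the plan; it is shown because power at 3 units is already near its ceiling.

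**A refinement on cost.** The 0.01-point loss counts only the degree of freedom. Randomization is not stratified by age, so chance imbalance also adds to the adjusted variance. On average the factor is about 1 + 1/114 = 1.009, which raises the SE by about 0.4% (0.679 to 0.682 at R² = 0). Simulation of 200,000 trials per scenario agrees: at R² = 0, power is 69.8-70.0% unadjusted and 69.4-69.5% adjusted at 2 units, and 97.6% against 97.5% at 3 units. The linear model therefore breaks even near R² of 1%, and the gains in the table shrink by about the same 0.4% of SE.

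**Stratified rank test instead.** Rank-sum against van Elteren at two-sided 0.017, scores rounded and limited to 0-28, difference 2 units, 20,000 runs per scenario (12,000 for R² of 0.01 and 0.02):

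| R² | Rank-sum | van Elteren |
|---|---|---|
| 0 | 66.1-66.3% | 64.8-65.1% |
| 0.01 | 66.2-66.3% | 65.4-65.8% |
| 0.02 | 65.4-66.6% | 65.1-66.3% |
| 0.05 | 66.0-66.2% | 67.3-67.4% |
| 0.10 | 65.9-66.0% | 70.0-70.2% |

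Van Elteren loses power at R² = 0 and breaks even only near R² of 2-3%. At 3 units and R² = 0 it has 95.9-96.2% against 96.5%.

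**The case against.** The strongest case against is that this is a preference, not a finding. The plan's analysis is valid and well powered, and the gain depends on an R² that appears nowhere in the documents. With 50-75% of patients aged 65 or over (assumed), an R² of 0.05-0.10 needs an OBAS gap between age groups of 3 × √(R²/[q(1 − q)]), with q the share aged 65 or over. That is about 1.3 to 2.2 units, or 45-73% of the effect the trial is built to detect. One preoperative dose of each drug is a weak reason to expect such a gap on POD 1, after floor care with scheduled acetaminophen and opioids titrated to pain.

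Age group is also only a proxy for receiving the drugs: creatinine clearance, contraindications and the anesthesiologist's discretion also decide. The cited pathway forms may hold a line for patients aged 65 and over that 6.1 does not show. Baseline pain, or type of arthroplasty, might predict OBAS better.

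All of this stands as a limit on the size of the gain. It does not defeat the linear-model suggestion, whose cost is close to nil if age is irrelevant. It does rule out extending the suggestion to the rank tests, where the loss is larger and the direction of benefit is unknown.

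**Conclusion.** The point holds as an optional, low-priority improvement confined to the linear model. Its benefit is a 2.5-5% narrower standard error if age group explains 5-10% of OBAS variance, and essentially nothing if age group explains about 1% or less. Both rest on the SD of 3, on 39 evaluable patients per arm, and on an age effect that the documents do not give.

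A reader might infer more than this, and the documents do not support it:

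- **Bias between arms.** The age limits are the same in both lists and allocation cannot affect age, so the unadjusted comparison is unbiased and keeps its alpha.
- **Inadequate power.** The 3-unit target already has about 96-98% power.
- **An open choice of covariate.** Section 7.2 names no covariate, so the plan leaves no such choice to close.
- **A need to stratify the rank tests or the randomization.** A stratified rank test can lower power, and no change in randomization is needed for the gain described.

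**What to change.** Before OBAS data are examined, add one sentence to 7.2: the OBAS comparison, overall at 0.05 and pairwise at 0.017, uses a linear model with terms for arm and age group (under 65, 65 and over). Keep the unadjusted Kruskal-Wallis test, with pairwise rank-sum tests, as the non-parametric analysis; do not replace them with van Elteren or a stratified Kruskal-Wallis test.

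The cost is that sentence and one model term from a variable already recorded. If age group is unrelated to OBAS, the loss is about 0.01 points of power from the degree of freedom, or about 0.4 points at 2 units and 0.1 at 3 units once chance imbalance is averaged in. Sample size, alpha and randomization stay as they are.

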6.2 Intra-Operative Plan

General anesthesia (induction with propofol and maintenance with isoflurane inhaled anesthesia with or without use of nitrous oxide (N₂O) and oxygen combination) with use of endotracheal tube, intraoperative monitoring (standard ASA monitoring), and supplemental analgesia. The covering anesthesiologist may also consider sevoflurane or desflurane as the inhalational anesthetic. Additional intraoperative monitoring such as continuous blood pressure via arterial line will be at the discretion of the attending anesthesiologist. Each patient will receive dexamethasone 8 mg IV⁴² and granisetron 0.1 mg or ondansetron 4 mg unless contraindicated (e.g. brittle diabetes defined as unpredictable and instable blood glucose levels with frequent episodes of hypoglycemia and/or ketoacidosis, or severe drug allergy defined as an immune reaction resulting in shortness of breath, hives, rash, blisters, anaphylaxis, wheezing, and fever). Other medications for nausea prophylaxis will be given at the discretion of the individual

anesthesiologist providing intraoperative care (which may include Droperidol 0.625 mg IV or Propofol infusion).

Intraoperative opioids will be administered at the discretion of the in-room anesthesia provider based on hemodynamic signs of pain such as increased blood pressure or heart rate. This may include but not limited to IV morphine, dilaudid, fentanyl, and ketamine.

All surgeries will be performed by two orthopedic surgeons at Mayo Clinic Hospital, Methodist Campus. All patients will receive a unilateral primary total shoulder arthroplasty, either anatomic or reverse TSA.

Typically, the decision to perform either an anatomic or reverse TSA is dependent on the function and stability of the rotator cuff muscles. The standard total shoulder arthroplasty involves a metal ball replacing the head of the humerus and a plastic implant used to replace the socket of the shoulder blade. In reverse total shoulder arthroplasty, the components are reversed. Limited available studies compare outcomes between standard total shoulder arthroplasty and reverse shoulder arthroplasty. In a recent study by Kiet and colleagues, outcomes between both groups were comparable, including pain.⁴³

If patients are randomized to the LIA group, periarticular injection will occur after implantation of the final prostheses, but prior to closure of the fascia. All surgeons will complete the infiltration following a similar protocol, equally distributing the study medication around the glenoid and humerus, subscapularis, deltoid, posterior capsule and subcutaneous tissue.

Regional Block – Both CISB and SISB:

Preoperatively, patients will be sedated, under the discretion of the anesthesiologist, with intravenous midazolam (1-4 mg) and fentanyl (50-200 mcg) for alleviation of anxiety and pain.

Patients randomized to either the CISB or SISB group will follow institutional practice in accordance to the total joint regional anesthesia pathway (MC1156-462rev0115). The interscalene nerve block will be performed under continuous live ultrasound guidance, obtaining visualization of the roots (C5-C6 is ideal) or trunks (Superior Trunk is ideal) of the brachial plexus in between the anterior and middle scalene muscles as described by Chan.⁴¹ An in plane or out of plane approach to needle advancement under live ultrasound guidance will be at the discretion of the anesthesiologist. In cases with poor ultrasound imaging, a combined nerve stimulator and ultrasound guidance technique is acceptable. Appropriate needle placement will be verified by injecting normal saline 0.9% and visualizing spread within the interscalene groove at the level of the roots/trunks of the brachial plexus. Local anesthetic may also be used for hydrodissection in order to navigate needle placement into the correct position. The proceduralist should attempt to use less than 10 mL (if possible) of saline 0.9% to identify correct placement of peripheral nerve block.

Regional Block – SISB

Once needle position is verified, the initial loading dose of local anesthetic solution to be administered is presented in Table 2.

Regional Block – CISB

Once needle position is verified by ultrasound imaging, a continuous catheter device will be placed within the interscalene groove at the level of the roots/trunks of the brachial plexus. After delivery of the catheter, verification of the catheter within the interscalene groove will be assessed by again evaluating spread of normal saline 0.9% or local anesthetic within the interscalene groove.

The initial loading dose of local anesthetic solution to be administered is presented in Table 2. The local anesthetic solution will be bloused through the catheter, and secured into place above the clavicle and away from the surgical field.

Brachial plexus block evaluation is as follows: sensory – sensation to cold over the deltoid muscle (0= absent or diminished, 1 = at baseline). Block will be assessed either preoperatively (at least 25 minutes after the placement of the block, if presurgical time permits), postoperatively in the recovery room, or patients room on POD 0. This assessment will be charted in the electronic anesthesia medical record when it has been completed.

Table 2: CISB and SISB Group – Bolus Injection

Nerve Blocked	Local Anesthetic	Concentration	Volume milliliters (mL)	- Adjuvants Added
Interscalene Brachial Plexus – CISB and SISB	Bupivacaine	0.5%	15 to 20 mL	1:200,000 Epinephrine

Continuous Interscalene Nerve Block (CISB):

The continuous interscalene nerve block catheter will be loaded in the PACU with bupivacaine 0.2% 10 milliliters (mL), and then an infusion will be initiated of bupivacaine 0.2% at 8 to 10 per hour. Infusion rate will be at the discretion of the pain service and attending anesthesiologist. The catheter will be discontinued on POD 1, unless surgeon requests catheter to remain in for a longer period of time.

Failed Block – CISB and SISB Group

In the event that a failed block were to occur, defined as intact or baseline sensation to cold over the deltoid muscle after 25 minutes since completion of block (pre-op) or pain at the surgical site along with intact or baseline sensation to cold over the deltoid muscle (post-op), the patient will be managed accordingly at the discretion of the covering anesthesiologist (which may include either re-blocking, or utilizing pain medications). Patient’s will still be involved in the study per intention-to-treat analysis.

Local Infiltration Analgesia (LIA):

The LIA group will utilize weight based dosing of Ropivacaine as part of a “cocktail” solution (Table 1), and will receive a total volume of 120 mL injected in the periarticular structures by the surgeon. This is a one-time injection. This will occur after implantation of the final prostheses,

but prior to closure of the fascia. All surgeons will complete the infiltration following a similar protocol, equally distributing the study medication around the glenoid and humerus, subscapularis, deltoid, posterior capsule and subcutaneous tissue. Medications and dosage of the LIA group is as follows:

Table 1: LIA Group

Drug	50-74.9kg	75-99.9 kg	100-125kg
Ropivacaine	200 mg	300 mg	400 mg
Epinephrine	100 mcg	200 mcg	300 mcg
Ketorolac	30 mg	30 mg	30 mg

*Normal Saline will be added to bring the total volume to 120 mL

Study Site: All surgeries included in this study will be performed at Mayo Clinic Hospital, Methodist Campus. Postoperative care will take place at the same hospital.

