1.1 Background

Background and Significance

Uncontrolled postoperative pain can be associated with significant deleterious consequences, including elevated stress response, decrease quality of life, increase in morbidity and mortality, and the potential for persistent post-surgical pain.¹ Total shoulder arthroplasty (TSA) is considered to be a major surgical procedure resulting in severe postoperative pain, especially in the first 48 hours after surgery.² Establishing a clinical pathway for total joint arthroplasty, utilizing a multi-modal analgesic approach including regional anesthetic techniques, appears to improve perioperative outcomes.³ The use of interscalene brachial plexus nerve block remains the cornerstone for analgesia following shoulder surgery in comparison to suprascapular nerve block, intra-articular injection, and intravenous opioids.^{4,5} Single injection interscalene blockade (SISB) provides adequate pain relief; however, no optimal dose has been identified and the duration of action is variable.⁶ Continuous interscalene nerve block (CISB) provides extended analgesia compared to SISB, suggesting its use may be more appropriate for moderate-to-severe painful shoulder procedures.^{7,8} Although analgesia following intra-articular and subacromial local anesthetic injections compared to interscalene brachial plexus block has shown to be less efficacious, variability includes operator experience, injection technique, medication solution with various adjuvants, and surgical procedure.^{9,10}

CISB has the potential to improve analgesia when compared to SISB; however, potential problems encountered include technical difficulty of catheter placement, increased procedure time, catheter dislodgement, leakage at the site of insertion, and developing an infrastructure to support the catheter.

With the advent of local infiltration analgesia (LIA)¹¹, there has been increasing interest in its use for total joint arthroplasty.¹²⁻¹⁴ Theoretical advantages would include comparable pain scores to regional anesthesia techniques, while minimizing motor and/or sensory blockade as well as complications seen with interscalene brachial plexus blocks. Another advantage would be to

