1.2 Investigational Technique and Agents

Local infiltration analgesia, developed by Kerr and Kohan, has only recently become a popular technique for postoperative analgesic control.¹¹ The proposed technique was developed for knee and hip joint replacement; therefore, most of the current literature utilizing local infiltration analgesia is for total hip and total knee replacements.^{12,14,18} There is limited literature utilizing local infiltration analgesia for total shoulder arthroplasty, hence the basis for this study. It is known that local infiltration analgesia involves injection of local anesthetic into the peri-articular tissues and intra-articular capsule in a systematic approach. Injection into the peri-articular tissue is thoughtfully considered, as injection of medication should be directed at tissues with high density of pain receptors.¹⁹ The two orthopedic surgeons have discussed with each other the peri-articular tissue areas of significance (a priori), which would provide the greatest postoperative analgesic control.

The local infiltration analgesia (LIA) group will receive a one-time injection of the “cocktail” solution (ropivacaine weight base dose mixed with epinephrine, ketorolac, and normal saline 0.9%), injected into the periarticular structures by the surgeons. This will occur after implantation of the final prostheses, but prior to closure of the fascia. All surgeons will complete the infiltration following a similar protocol, equally distributing the study medication around the glenoid and humerus, subscapularis, deltoid, posterior capsule and subcutaneous tissue.

Bupivacaine and Ropivacaine are amide local anesthetics which inactivates voltage gated sodium channels. In nerves, this results in loss of action potential and signal conduction along the nerve fiber leading to sensory and/or motor blockade. Bupivacaine and Ropivacaine are considered to be a long acting local anesthetic, and is indicated for multiple uses including local infiltration and peripheral nerve block.^{20,21}

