5.3 Method for Assigning Subjects to Treatment Groups

The treatment allocation will be performed using a randomization schedule which will be created by the Division of Biomedical Statistics and Informatics. This randomization schedule will be generated using a SAS program (SAS version 9.3, SAS Institute Inc, Cary NC) with randomization performed in blocks of size N=6 to ensure that after every sixth patient is enrolled there are an equal number of patients assigned to each of the 3 treatment conditions. Using this randomization schedule, an EXCEL spreadsheet application will be created which will include sequentially assigned subject-ID numbers and corresponding treatment assignments. When a patient is enrolled they will be assigned the next sequential subject-ID number and a member of the anesthesia clinical research unit, who will be different from the care team and are not involved in the medical management of the patient, will use the online system to retrieve the allocated treatment assignment for this subject-ID.

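### Two surgeons perform every operation and inject the LIA solution, but the OBAS analysis has no surgeon term; pre-specifying one is a cheap improvement with a small expected gain.

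*Combined protocol and SAP*

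**What the plan says.** - **Operators.** Section 6.2: "All surgeries will be performed by two orthopedic surgeons". Section 1.2 has the LIA solution "injected into the periarticular structures by the surgeons", so the surgeon operates in all three arms and also delivers the study treatment in one.
- **Standardisation.** Section 1.2: "The two orthopedic surgeons have discussed with each other the peri-articular tissue areas of significance (a priori". Section 6.2: "All surgeons will complete the infiltration following a similar protocol", and it lists the structures to be infiltrated.
- **Allocation.** Section 5.3 describes one schedule, "randomization performed in blocks of size N=6", and names no stratification factor.
- **Analysis.** Under section 7.2 the outcome (OBAS, from the context) "will be compared across groups using ANOVA (or the Kruskal-Wallis test", followed by pairwise tests at 0.017. No covariate or stratum is named.
- **Elsewhere.** The subgroup analyses in section 7.3 are patients treated per protocol and reverse versus anatomic arthroplasty. Surgeon is not among the baseline variables named in section 6.1, although the schedule in section 6.3 includes a line for surgical data.

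**The concern.** Section 1.1, on earlier comparisons of intra-articular and subacromial injection with interscalene block, notes that "variability includes operator experience, injection technique, medication solution with various adjuvants, and surgical procedure". This trial compares joint infiltration with interscalene block, with two operators, and surgeon is a known two-level factor fixed before surgery.

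If the two surgeons' patients differ in OBAS whatever the arm, a one-way analysis leaves that difference in two places: the residual variance, and any chance imbalance in surgeon share between arms. The remark in section 6.2 that outcomes were comparable concerns implant type, so it gives no reason to ignore surgeon. At stake is some precision in the three pairwise contrasts, and the credibility of a surgeon adjustment if one is added only after data from an unblinded trial have been seen.

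**Working it through.** **Inputs from the documents (section 7.1):** target difference 3 OBAS units, SD 3, 39 evaluable and 43 randomised per arm, two-sided alpha 0.017. **Assumed, because the documents are silent:** caseload split 50:50 (70:30 as a check) and a surgeon gap g of 0.5 to 3 OBAS units.

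**1. The plan's own figure.** SE of a contrast = 3 × √(2/39) = 0.679. Power by the noncentral t is 97.4%, or 96.7% with n scaled by the rank test's relative efficiency of 0.955. The stated power above 90% is reproduced, with room to spare.

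**2. Chance imbalance.** With surgeon share p, the SD of the difference in share between two arms of 43 is √(2p(1−p)/43).
- p = 0.5: √(0.5/43) = 0.108
- p = 0.7: √(0.42/43) = 0.099

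Simulating 20,000 trials of 129 patients in blocks of 6 gave 0.108 and 0.099. A gap above 20 points in one named contrast occurs in about 6% of trials (4.6% at 70:30). A gap that large between some pair of the three arms occurs in about 15% (11% at 70:30).

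**3. Shift in a contrast.** Typical (1 SD) shift = g × 0.108: 0.11 units for g = 1 and 0.22 for g = 2. Against the SE of 0.679 that is 0.16 and 0.32 of a standard error. The 95th-percentile shift for g = 1 is 0.21 units.

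**4. What adjustment gains.** If 3 is the total SD, the within-surgeon SD is √(9 − g²/4) at a 50:50 split, and adjusted SE ≈ √(9 − g²/4) × √(2/39). If 3 is the within-surgeon SD, the adjusted SE stays at 0.679 and the unadjusted SE is √(9 + g²/4) × √(2/39). Power below is by the noncentral t, ignoring the small loss from realised imbalance.

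| g | SD 3 is total: SE | power | SD 3 is within surgeon: SE | power |
|---|---|---|---|---|
| 1 | 0.679 → 0.670 | 97.4% → 97.8% | 0.689 → 0.679 | 97.0% → 97.4% |
| 1.5 | 0.679 → 0.658 | 97.4% → 98.2% | 0.700 → 0.679 | 96.5% → 97.4% |
| 2 | 0.679 → 0.641 | 97.4% → 98.6% | 0.716 → 0.679 | 95.8% → 97.4% |
| 3 | 0.679 → 0.588 | 97.4% → 99.6% | 0.760 → 0.679 | 93.2% → 97.4% |

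Simulation (6,000 two-arm trials per setting; run for g = 0, 0.5, 1, 1.5 and 3) agrees. At g = 3 with within-surgeon SD 3, power was 93% (t) or 91% (rank-sum) unadjusted and 98% adjusted.

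**5. Validity without the term.** In the same simulations the unadjusted type I error lay between 0.013 and 0.020 around the nominal 0.017, with mean bias about zero.

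**6. Precision of by-surgeon contrasts.** With 39 per arm split equally, each surgeon has 19.5 per arm. The SE of one surgeon's contrast is 3 × √(2/19.5) = 0.961, a 95% half-width of 1.9 units. The difference between the two surgeons' contrasts has a half-width of 1.96 × 0.961 × √2 = 2.7 units (2.9 at 70:30), against a target of 3.

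**The case against.** The strongest reply is that nothing here is an error. Allocation is random, so surgeon imbalance is random too, and its contribution is already inside the unadjusted standard error. The shift in step 3 and the gain in step 4 are one source of noise seen from two sides, not two separate costs. Surgeon was not a stratification factor, so the analysis is not obliged to carry it. All of this stands.

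The protocol also deals with operator variation by procedure: agreed injection areas and a similar infiltration protocol. The sentence in section 1.1 describes earlier literature, not this trial. That stands as mitigation for LIA delivery, but it does not cover differences in the surgery itself.

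Block placement varies by operator as well: section 6.2 leaves the needle approach and infusion rate to the anesthesiologist or pain service and gives the bolus as a range. A surgeon term does nothing about that. This stands, although surgeon is the operator factor that is present in every arm and has only two levels.

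Three stronger readings are tempting, and the documents do not support them:
- **That the arm comparisons are biased or the test invalid.** Step 5 shows otherwise.
- **That a surgeon term removes differences in how each surgeon delivers LIA.** Those arise only in the LIA arm, so they are an arm-by-surgeon interaction. An additive term removes only the main effect.
- **That by-surgeon results would show whether a poor LIA result reflects the technique or one operator.** Step 6 shows they are too imprecise, unless the operators differ enormously.

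**Conclusion.** The point holds as a minor improvement to the analysis, not as a defect that threatens the conclusions. The OBAS analysis omits a two-level factor that is fixed before surgery and can be adjusted for at almost no cost. The omission does not affect type I error or cause systematic bias.

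For assumed surgeon gaps of 1 to 2 OBAS units, the typical shift in a contrast is 0.11 to 0.22 units against an SE of about 0.68, and adjustment adds about 0 to 2 points of power. Only an extreme gap of 3 units makes the gain noticeable, at about 2 to 7 points, where the upper end sets an unadjusted rank test against the adjusted linear model. These figures rest on the SD of 3 in section 7.1, the assumed caseload split and the assumed surgeon gap. If the surgeons do not differ, nothing is lost beyond one degree of freedom.

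The 15% chance of a 20-point gap somewhere among three arms should not be read as the risk to a given comparison; for one named contrast it is about 6%.

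**What to change.** Record the operating surgeon as a named variable. In section 7.2, specify the primary OBAS analysis as a two-factor ANOVA (arm, surgeon) with the pairwise arm contrasts taken from that model. If the non-parametric route is used, replace the Kruskal-Wallis and rank-sum tests with surgeon-stratified (van Elteren type) rank tests. Fix this before outcome data are examined.

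The CISB–LIA and SISB–LIA differences may be shown by surgeon with confidence intervals, labelled descriptive and with a statement that they cannot separate technique from operator.

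The cost is wording, one degree of freedom and a slightly less simple rank test. N is unchanged.

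I would not add separate randomisation lists per surgeon. Section 5.7 makes the trial unblinded and section 5.3 fixes the block size at 6, so each surgeon would see every assignment on his or her own list and could follow the blocks more easily than on one merged list. Using recruiters and allocation staff outside the care team (sections 4.3 and 5.3) limits that risk but does not remove it, and model adjustment deals with main-effect imbalance without it.
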